1. LIST OF ABBREVIATIONS AND DEFINITIONS OF TERMS

ADR	Adverse Drug Reaction
AE	Adverse Event
ALP	Alkaline Phosphatase
ALT(=SGPT)	Alanine Transaminase
ANCOVA	Analysis of Covariance
ANOVA	Analysis of Variance
AST(=SGOT)	Aspartate Transaminase
BMI	Body Mass Index
BUN	Blood Urea Nitrogen
СТ	Computed tomography
CS	Clinically Significant
ECOG	Eastern Cooperative Oncology Group
eGFR	Estimated Glomerular Filtration Rate
FAS	Full Analysis Set
γ-GTP(=γ-GT)	Gamma-glutamyl transpeptidase (Gamma-glutamyl transferase)
Hb	Hemoglobin
Hct	Hematocrit
IWRS	Interactive Web Response System
LSM	Least-Square Mean
MedDRA	The Medical Dictionary for Regulatory Activities
NCS	Not Clinically Significant
PPS	Per-Protocol Set
PT	Preferred Term
RBC	Red Blood Cell
SAE	Serious Adverse Event
SE	Standard Error
SOC	System Organ Class
TEAE	Treatment-Emergent Adverse Event
UDCA	Ursodeoxycholic acid
WBC	White Blood Cell
WHO	World Health Organization

Protocol No.: DW_UDCA005 English Translation Version

2. INTRODUCTION

As domestic incidences of cancer continue to rise, gastric cancer is the second most common cancer accounting for 17.2% of total cancer incidences. In particular, it is the most common type of cancer in men, occurring more frequently than prostate cancer and colon cancer. Furthermore, due to early screening and the development of treatment techniques, the 5-year survival rate of patients with gastric cancer has been increasing every year. Therefore, there is a trend of decrease in complications for these patients due to treatment and a growing interest in improving their quality of life.

Currently, surgical treatment, chemotherapy, and radiation therapy are performed to treat gastric cancer. To date, surgical treatment is known to be the most fundamental and effective method for increasing the survival rate. Thus, the standard treatment for gastric cancer is surgery if a radical resection is possible. However, due to various causes such as anatomical changes after gastrectomy, major complications have been reported including alkaline reflux gastritis, reflux esophagitis, iron deficiency anemia, vitamin B_{12} deficiency, metabolic bone disease, and cholelithiasis.

The proportion of patients with gallstone formation has been reported to be approximately 13%-17% within 1 year and 20% within 5 years after gastrectomy, and this is about 10% higher than the prevalence of gallstones in the general population (2.0% in Korea and 3.2% in Japan). The reason for the increased incidence of gallstones after gastrectomy is unclear. The predominant hypothesis is that the anatomical changes resulting from the surgery, especially in the event the vagus nerve is severed, affect contractility of the gallbladder, causing stasis and supersaturation of the bile that promote gallstone formation. In fact, the incidence of gallstones in patients who underwent pylorus-preserving gastrectomy is significantly low, supporting such hypothesis.

The gallstone prevention effect of UDCA, like the gallstone dissolution methods, are known to be manifested by suppressing supersaturation of cholesterol, which is a factor of gallstone formation, reducing nucleating factors, and improving gallbladder motility. The effect of oral administration of UDCA is an increase in bile reservoir and changes in bile acid composition, thereby suppressing the saturation of cholesterol through reducing cholesterol saturation in the gallbladder, intestinal cholesterol absorption, and cholesterol secretion in the bile. It has also been reported that it reduces nucleating factors such as glycoprotein in bile and improves gallbladder motility by affecting gallbladder contractility.

Since the gallstone prevention effect of UDCA is related to its inherent function as a tertiary bile acid, in addition to obese patients who have experienced rapid weight loss, it is expected to be effective in prevention of gallstone formation in patients with gastric cancer who underwent gastrectomy. However, to date, there has been no study on the effect of UDCA on the prevention of gallstone formation after gastrectomy for patients with gastric cancer. Therefore, Daewoong Pharmaceutical Co., Ltd. developed DWJ1319 with UDCA 300 mg as the active substance and planned a phase 3 clinical study to evaluate the efficacy and safety of DWJ1319 for the prevention of gallstone formation in patients with gastric cancer who underwent gastrectomy.

Protocol No.: DW_UDCA005 English Translation Version

3. STUDY OBJECTIVES

3.1 Primary Objective

To assess the efficacy of DWJ1319 300 mg or DWJ1319 600 mg administered once daily for 52 weeks in the prevention of gallstone formation after gastrectomy in patients with gastric cancer compared with placebo.

3.2 Secondary Objective

To assess the safety and tolerability of DWJ1319 300 mg or DWJ1319 600 mg administered once daily for 52 weeks compared with placebo.

Protocol No.: DW_UDCA005 English Translation Version

4. INVESTIGATIONAL PLAN

4.1 Overall Study Design and Plan

A multi-centered, randomized, double-blind, placebo-controlled, phase 3 clinical study. The subjects are patients who have been diagnosed with gastric cancer and underwent gastrectomy for treatment. Screening will be conducted on subjects who gave an informed consent to participate in the clinical study. Subjects who meet the inclusion criteria and do not meet exclusion criteria will be randomly assigned to DWJ1319 300 mg (DWJ1319 300 mg, once a day), DWJ1319 600 mg (DWJ1319 300 mg, twice a day), or placebo (1: 1: 1). For randomization, stratified randomization using the study site, the lymph node resection range (D1+, D2), and the type of gastrectomy as the stratification factors will be performed and randomization will be performed within 2 weeks from gastrectomy. During the study period, the subjects will visit the study site at screening, randomization (Day 1) and at 3-month intervals after the administration of investigational product (at 3, 6, 9, and 12 months) to undergo protocol-specified tests and procedures at each visit. However, any subject with formation of gallstone confirmed during the treatment period will terminate the study at the time of confirmation.

Visit 1	Visit 2	Visit 3	Visit 4	Visit 5	Visit 6		
Until week -2	Day 1	3 months±1 week	6 months±1 week	9 months±1 week	12 months±1 week		
Screening	Randomizatio n	Treatment period					

4.2 Study Duration

The overall duration of this study is expected to be about 20 months, however, there may be a change in the duration if a situation arises that may affect the progress of the clinical study such as difficulties in selecting the subjects.

Study duration for each subject: About 54 weeks as follows.

Screening period: 2 weeks

• Treatment period: 52 weeks (12 months)

4.3 Dosage, Administration and Schedule

All randomly assigned subjects are orally administered with the investigational product twice a day, one capsule at a time, for a total of 52 weeks. The subjects take the investigational product in the morning and evening according to the investigator's instructions and if possible, take it at the same time each day.

Protocol No.: DW_UDCA005 English Translation Version

[Method of administration by treatment group]

Treatment group	Method of administration	Study drug
Placebo	One capsule each of placebo for DWJ1319 in the morning	Morning: ○,
1 lacebo	and evening	Evening: ○
DWJ1319 300 mg	One capsule each of placebo for DWJ1319 in the morning	Morning: ○,
DW31319 300 Hig	and DWJ1319 in the evening	Evening: ●
DWJ1319 600 mg	One capsule each of DWJ1319 in the morning and	Morning: ●,
DVV31319 000 111g	evening	Evening: ●

o: Placebo for DWJ1319, ●: DWJ1319

4.4 Randomization and Unblinding

4.4.1 Randomization

Randomization is performed to ensure the scientific validity of the clinical study, to reduce bias that may occur during the clinical study, and to prevent the investigator's subjectivity in assigning subjects to each treatment group.

Based on the stratification factors, stratified block randomization method is used to randomly assign subjects to DWJ1319 300 mg, DWJ1319 600 mg, and placebo at 1:1:1 ratio. This will be done by each study site conducting the clinical study using the SAS proc plan procedure.

Each stratification factor will be set with two levels as below:

- Lymph node resection range: D1+, D2
- Type of gastrectomy: Total gastrectomy, partial gastrectomy

The procedure for assigning test subjects to each treatment group and prescribing and distributing the investigational product is as follows:

When the subjects are enrolled on Day 1, the investigator assigns to each subject a randomization number based on the pre-generated randomization results, via the interactive web response system (IWRS). The investigator prescribes the investigational product using the randomization number and the pharmacist distributes the investigational product with the same assigned number to the subject.

The randomization number of a subject withdrawn from the study will also be withdrawn but retained. New subjects must be assigned new screening numbers and randomization numbers.

4.4.2 Unblinding

This clinical study maintains a blind on the type of drug assigned to each subject on the investigator and subject. By maintaining the double-blinding on both the investigator and subject, it allows the investigator or subject to avoid bias in assessing treatment effects and adverse reactions. The study drug and the comparator in this clinical study should be manufactured in the same form so that it cannot be visually distinguishable for the double-blinding. The sub-portion packaging should also be the same.

If it is deemed necessary to remove the blinding due to the occurrence of an emergency

Protocol No.: DW_UDCA005 English Translation Version

situation that threatens the safety of the subject, the investigator should immediately notify Daewoong Pharmaceutical Co., Ltd. or the monitoring staff of the contract research organization delegated by Daewoong Pharmaceutical Co., Ltd. The monitoring staff is obliged to immediately contact the representative of Daewoong Pharmaceutical Co., Ltd. After obtaining the relevant information, the representative of Daewoong Pharmaceutical Co., Ltd. will discuss with the investigator to decide whether to remove the blinding and document the decision. After consulting with the sponsor, the investigator will access the unblinding screen of the randomization website, input necessary information, obtain information on the investigational product of the subject, print the screen, sign it, and keep it under the investigator's file.

In the event that it is impossible to immediately contact Daewoong Pharmaceutical Co., Ltd., the sponsor, the investigator will access the unblinding screen of the randomization website, input necessary information, obtain information on the investigational product of the subject, print the screen, sign it, and keep it under the investigator's file. In such case, the investigator must notify Daewoong Pharmaceutical Co., Ltd. as soon as possible of the unblinding of the double-blind, and document the reasons for unblinding without consulting the sponsor.

If the investigator finds out the subject's code during the study, the investigator should endeavor to eliminate bias in assessing efficacy and safety.

After completing the study, the investigator will resolve any issues on all data through the Data Clarification Form (DCF). Once the database is confirmed to be complete and accurate, the data will be locked and randomization code information will be released. Subsequent changes to the database are possible only with the written consent of the sponsor and the database administrator.

4.5 Schedule of Study

The clinical study is conducted according to the following schedule.

	Screening	Baseline	Treatment			
	Visit 1	Visit 2	Visit 3	Visit 4	Visit 5	Visit 6 / Early terminatio n ¹⁾
Duration	From Week - 2 Day - 1	Day 1	Month 3 (±1 week)	Month 6 (±1 week)	Month 9 (±1 week)	Month 12 (±1 week)
Informed consent ²⁾	0					
Demographic survey	0		O ³⁾	O ³⁾	O ³⁾	O ³⁾
Medical history/prior surgery	0	0				
Physical examination	0			0		0
Vital signs	0	0	0	0	0	0
Inclusion/exclusion criteria	0	0				
Randomization		0				
Abdominal ultrasound ⁴⁾	O ⁵⁾		0	0	0	0

Protocol No.: DW_UDCA005 English Translation Version

	Screening	Baseline	Treatment			
	Visit 1	Visit 2	Visit 3	Visit 4	Visit 5	Visit 6 / Early terminatio n ¹⁾
Duration	From Week - 2 Day - 1	Day 1	Month 3 (±1 week)	Month 6 (±1 week)	Month 9 (±1 week)	Month 12 (±1 week)
Abdominal CT scan ⁶⁾	O ⁵⁾			0		0
Assessment of bile reflux symptoms		0	0	0	0	0
Upper gastrointestinal endoscopy ⁶⁾			0			0
Laboratory tests	O ⁷⁾		O ⁸⁾	0	O ⁸⁾	0
Pregnancy test ⁹⁾	0					
Prescription of investigational product		0	0	0	0	
Treatment compliance			0	0	0	0
Adverse events			0	0	0	0
Prior/concomitant medications ¹⁰⁾	0	0	0	0	0	0

- 1) For a withdrawal or early termination, the procedures for Visit 6 will be performed.
- 2) The informed consent form will be obtained in writing prior to study initiation after explaining the objectives and details of the study to the subjects. The informed consent should be obtained prior to any study procedures.
- 3) At the screening visit, the demographics (subject initials, sex, date of birth, smoking status and alcohol use, weight, height, BMI, etc.) will be collected. Thereafter, only weight will be measured at each visit.
- 4) The measuring will be conducted in a fasted state (including the investigational product) on the day of visit. If not in a fasted state on the day of visit, the subject will revisit within the imaging test window (regular visit ± 2 weeks) to carry out the examination. A subject with confirmed gallstone formation during the study period will terminate the study at the time of confirmation.
- 5) If there is a recent imaging test result (within 6 weeks before screening), the result can be used as a screening test result.
- 6) Abdominal CT and upper gastrointestinal endoscopy (once every 3 months or 12 months) are routine tests that are usually performed in association with gastrectomy. If there is a result of such tests, the results of the routine tests are collected and used without performing additional testing.
- 7) For any screening test result not meeting the inclusion/exclusion criteria, only one re-test is allowed.
- 8) At Visits 3 and 5, Liver function tests (ALT, AST, ALP, γ-GTP, and total bilirubin) among laboratory tests will be performed.
- 9) Urine HCG test will be performed only in women of childbearing age and the result should be confirmed prior to the administration of the investigational product.
- 10) Any drug that has been administered from 4 weeks before the screening visit throughout the study or is currently administered should be recorded.

4.6 Determination of the Sample Size

1) Number of Subjects to be Recruited

Taking into account the 20% withdrawal rate, this clinical study plans to enroll a total of 519 subjects (173 per group).

Protocol No.: DW_UDCA005 English Translation Version

2) Calculation Basis

The primary objective of this study is to assess the efficacy of the study drug compared with placebo in preventing gallstone formation after gastrectomy in patients with gastric cancer. If the efficacy of DWJ1319 300 mg or 600 mg versus placebo is statistically significant, the study drug is considered to demonstrate its superiority. The endpoint is the percentage of subjects forming gallstones within 12 months of gastrectomy. The hypothesis to test this is as follows:

 H_0 (Null hypothesis): $P_{T1} = P_C$ and $P_{T2} = P_C$ H_1 (Alternative hypothesis): $P_{T1} \neq P_C$ or $P_{T2} \neq P_C$

P_{T1}: Proportion of subjects forming gallstones after taking 600 mg of DWJ1319

P_{T2}: Proportion of subjects forming gallstones after taking 300 mg of DWJ1319

P_C: Proportion of subjects forming gallstones after taking placebo

For testing of each treatment group versus the placebo, the significance level of the test is not corrected because a sequential multiple test (twice) is performed using the fixed sequece method. The test sequence is 600 mg of DWJ1319 versus placebo and 300 mg of DWJ1319 versus placebo.

The following results were referenced to calculate the number of subjects to be tested.

	Placebo	Ursodiol	Ursodiol	Ursodiol	
Placebo		300 mg	600 mg	1,200 mg	
Study 1 (6M)	32.14% (18/56)	13.21% (7/53)	1.64% (1/61)	6.35% (4/63)	
Study 2 (12M)	16.94% (112/661)	-	-	-	
Study 3 (12M)	13.64% (6/44)	-	-	-	

In this clinical study, the incidence of gallstones with placebo was estimated to be 18%, which is the weighted average of study 1, 2 and 3, where study 1 is the result of placebo in obese patients who underwent gastrectomy and studies 2 and 3 are the adjusted results of placebo in patients with gastric cancer who underwent gastrectomy. Since it is difficult to estimate the incidence of gallstone of DWJ1319 by each dose, 7%, which is the weighted average of the three Ursodiol treatment groups in study 1, was estimated as the rate of gallstone formation for the study drug.

In addition to the above assumptions, the significance level is 5% for two-sided test, 80% for test power, and the minimum number of subjects for 1:1:1 assignment is as follows.

$$\begin{split} N &= \frac{\left(Z_{1-2/\alpha} + Z_{1-\beta}\right)^2 \left\{P_T(1-P_T) + P_C(1-P_C)\right\}}{\delta^2} \\ &= \frac{(1.96 + 0.842)^2 \left\{0.07(1-0.07) + 0.18(1-0.18)\right\}}{(0.07 - 0.18)^2} \approx 138 \end{split}$$

Protocol No.: DW_UDCA005 English Translation Version

The minimum number of subjects required to have a power level of 80% at the 5% significance level is calculated as 138 per group. Taking into account the 20% withdrawal rate, this clinical study plans to enroll 173 people per group (total of 519).

Protocol No.: DW_UDCA005 English Translation Version

5. ANALYSIS SETS

The validity data obtained from the subjects of this clinical study are analyzed in two forms, Full Analysis Set (FAS) and Per Protocol Set (PPS). Data on efficacy is analyzed using both FAS and PPS, and the final determination of efficacy endpoints is done by FAS analysis. Safety assessment is conducted on safety set.

5.1 Screened Set

It includes all subjects who have signed an informed consent and have been given a screening number.

5.2 Randomized Set

It includes all subjects randomized to the treatment groups.

5.3 Full Analysis Set (FAS)

Of the subjects which were administered the investigational product at least once after being randomized, the assessment will be conducted on those subjects that did not violate the inclusion/exclusion criteria, and had at least one evaluation for gallstone formation after randomization.

5.4 Per-Protocol Set (PPS)

The PP analysis set is composed of subjects who have completed the test without any serious deviation of the protocol that could affect the efficacy of the FAS analysis set. The subjects to be terminated according to the early termination criteria of Protocol 13.2 are included in the PP analysis set. The subjects who are excluded from the PP analysis set due to other serious deviations will clarify and the reasons will be documented prior to unblinding.

[Protocol 13.2 Early Termination of Clinical Study]

Subjects who have been confirmed to have gallstone formation by abdominal ultrasound during the post-randomization study drug administration period should stop participating in the clinical study at the time of such confirmation and perform a final assessment according to the Visit 6/early termination schedule. The subjects who finished early according to the early termination criteria are considered to have completed the clinical study according to the protocol, not withdrawn.

5.5 Safety Set

It includes all subjects administered with the investigational product at least once after being randomized.

Protocol No.: DW_UDCA005 English Translation Version

6. DOCUMENTATION OF VARIABLES

6.1 Efficacy Variables

6.1.1 Primary Endpoint

The primary efficacy endpoint of this study is the percentage of subjects with gallstone formation within 12 months of gastrectomy based on the external investigator's assessment. At such point, whether or not gallstones are formed is determined by adopting the assessment result agreed on by two or more of the three external investigators.

- Percentage of subjects with gallstone formation (%) = (Based on external investigator's assessment, the subjects who were identified as having gallstone formation in at least one of the following sites, gallbladder, bile duct, and intrahepatic bile duct, within 12 months after gastrectomy*/Number of subjects analyzed)*100
 - * In the case of the subjects who are confirmed to have gallstones by the institutional reviewer and are terminated early from the clinical study, to be conservative, they are defined as subjects with gallstone formation regardless of the external investigator's assessment.

[Protocol 11.2.7 Determination of Gallstones]

The diagnosis of gallstone formation is based primarily on the results of abdominal ultrasound and is supplemented by abdominal CT scan results. If the results of the two tests differ, abdominal ultrasound result should be considered first for gallbladder gallstones, and both abdominal ultrasound and abdominal CT should be considered in the case of bile duct gallstones or intrahepatic bile duct gallstones. If only the abdominal CT scan result is available, utilize the available CT scan result for the diagnosis of gallstone formation.

If the following criteria are satisfied as a result of abdominal ultrasound, make a diagnosis as gallbladder gallstone. If any one of the criteria is not met or there is only hyperechoic shadow without posterior acoustic shadow, it is judged negative for gallstone formation.

- 1) Hyperechoic shadow (echo sign)
- 2) Posterior acoustic shadow
- 3) The movement of echo according to changes in body position (movement, gravitational dependence)

The bile duct gallstone is distinguished by abdominal ultrasound that shows a hyperechoic substance with posterior acoustic shadow or an enlargement of peripheral bile duct around the echo, and is determined by compiling the results of abdominal CT scans.

Gallstones should be distinguished from biliary sludge and should be determined to be biliary sludge if the following criteria are met:

Protocol No.: DW_UDCA005 English Translation Version

- 1) Hypoechoic shadow without accompanying acoustic shadow
- 2) Moves according to changes in body position and has a characteristic to form a horizontal plane

The investigator will document in the case report form (CRF) the presence of gallstones, the presence of biliary sludge, and the location of gallstones (gallbladder, common bile duct, intrahepatic bile duct), size and number of gallstones.

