8.3. Targeted Number of Subjects and Justification

1) Number of Subjects to be Recruited

Taking into account the 20% withdrawal rate, this clinical study plans to enroll a total of 519 subjects (173 per group).

2) Calculation Basis

The primary objective of this study is to assess the efficacy of the study drug compared with placebo in preventing gallstone formation after gastrectomy in patients with gastric cancer. If the efficacy of DWJ1319 300 mg or 600 mg versus placebo is statistically significant, the study drug is considered to demonstrate its superiority. The endpoints are the proportion of subjects with gallstone formation within 12 months after gastrectomy. The hypothesis to test this is as follows:

$$H_0$$
 (null hypothesis): $P_{T1} = P_C$ and $P_{T2} = P_C$
 H_1 (alternate hypothesis): $P_{T1} \neq P_C$ or $P_{T2} \neq P_C$

P_{T1}: Proportion of subjects with gallstone formation after receiving 600 mg of DWJ1319

P_{T2}: Proportion of subjects with gallstone formation after receiving 300 mg of DWJ1319

Pc: Proportion of subjects with gallstone formation after receiving placebo

For testing of each treatment group versus the placebo, the significance level of the test is not corrected because a sequential multiple test (twice) is performed using the fixed sequential method. The test sequence is 600 mg of DWJ1319 versus placebo and 300 mg of DWJ1319 versus placebo.

The following results were referenced to calculate the number of subjects to be tested.

	Placebo	Ursodiol	Ursodiol	Ursodiol
	1 100000	300 mg	600 mg	1,200 mg
Study 1 ¹⁹⁾ (6M)	32.14% (18/56)	13.21% (7/53)	1.64% (1/61)	6.35% (4/63)
Study 2 ⁴⁾ (12M)	16.94% (112/661)	-	-	-
Study 3 ⁷⁾ (12M)	13.64% (6/44)	-	-	-

In this clinical study, the incidence of gallstones in placebo was estimated to be 18%, which is the weighted average of Studies 1, 2 and 3, where Study 1 is the result of placebo in obese patients who underwent gastrectomy and Studies 2 and 3 are the adjusted results of placebo in gastric cancer patients who underwent gastrectomy. Since it is difficult to estimate the incidence of gallstone of DWJ1319 by each dose, 7%, which is the weighted average of the three Ursodiol treatment groups in Study 1 was estimated as the rate of gallstone formation for the study drug.

In addition to the above assumptions, the significance level is 5% for two-sided test, 80% for test power, and the minimum number of subjects for 1:1:1 assignment is as follows:

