11.2.8. External Investigator's Assessment of the Imaging Test Results for Gallstone Formation

To ensure the reliability of the imaging test results (abdominal ultrasound and abdominal CT scan), independent external investigators evaluate the results of imaging tests to determine whether gallstones have formed. External investigators consist of three independent investigators who have not participated in the corresponding clinical study.

The external committee member will independently check the results of the imaging test without any exchange of opinions and state whether gallstones have formed or not. The assessment is based on abdominal ultrasound and CT imaging data collected from all study sites and is randomly arranged regardless of the number or the order of the visit of the subjects so that researchers can conduct an assessment without being affected by the time of shooting. The assessment results on which at least two of the three external investigators agree on will be selected.

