14.4. Efficacy Analysis

14.4.1. Primary Efficacy Endpoint

The primary efficacy endpoint is the percentage of patients with gallstone formation within 12 months after gastrectomy according to the assessment by an external investigator.

For the superiority testing of DWJ1319 over placebo on the incidence of gallstone formation, the sequential multiple testing will be performed for each treatment group according to the fixed sequence method.

- Step 1: Superiority testing for DWJ1319 600 mg compared with placebo (5% significance level)
- Step 2: Superiority testing for DWJ1319 300 mg compared with placebo (5% significance level)

As DWJ1319 600 mg is expected to be relatively more effective in preventing gallstones compared to DWJ1319 300 mg, the efficacy assessment of DWJ1319 600 mg versus placebo is given priority.

The step 2 test can be performed only if the result of step 1 test is statistically significant, and the conclusions about the superiority of DWJ1319 over placebo will be drawn based on the test result from each step. If the result of step 1 test is not statistically significant, the step 2 test will not be performed, and it will be concluded that both treatment groups of DWJ1319 have failed to demonstrate the superiority over placebo.

The test in each step will use the logistic regression model with the lymph node resection range and the method of gastrectomy as covariates and present the frequency and proportion along with 95% confidence interval of subjects who have formed gallstone within 12 months by treatment group.

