6.1.2 Secondary Endpoints

The secondary efficacy endpoints of this study are as follows:

- 1) Percentage of subjects forming gallstones within 3, 6, 9, and 12 months from gastrectomy
- ➤ Percentage of subjects with gallstones formation (%) = (The subjects who were identified as having gallstone formation in at least one of the following sites, gallbladder, bile duct, and intrahepatic bile duct, within 3, 6, 9, and 12 months after gastrectomy/Number of subjects analyzed)*100
- 2) Percentage of subjects forming gallstone within 3, 6, and 9 months from gastrectomy as assessed by the external investigator
- Percentage of subjects with gallstone formation (%) = (Based on external investigator's assessment, the subjects who were identified as having gallstone formation in at least one of the following sites, gallbladder, bile duct, and intrahepatic bile duct, within 3, 6, and 9 months after gastrectomy/Number of subjects analyzed)*100
- 3) Percentage of subjects forming biliary sludge within 3, 6, 9, and 12 months from gastrectomy
- ➤ Percentage of subjects with biliary sludge formation (%) = (The subjects who were identified as having biliary sludge formation at least once within 3, 6, 9, and 12 months after gastrectomy/Number of subjects analyzed)*100
- 4) Time to gallstone formation
- The time to gallstone formation is calculated as the time until the early termination or completion after a gastrectomy, if the gallstone has been formed within 12 months resulting in early termination, or at 12 months resulting in completion. Subjects who do not form gallstones until the completion of the clinical study are treated as censoring and their time period until completion is calculated. If subjects are withdrawn within the 12 months after a gastrectomy, they are treated as censoring data and their time period until the withdrawal is calculated.

^{*} In the case of the subjects who are confirmed to have gallstones by the institutional

Form DA-05-03.03 Statistical Analysis Plan

Sponsor: Daewoong Pharmaceutical Co., Ltd.

Protocol No.: DW_UDCA005 English Translation Version

reviewer and are terminated early from the clinical study, to be conservative, they are defined as subjects with gallstone formation regardless of the external investigator's assessment.

- Time to Gallstone Formation
 - Status = 1, if gallstones were formed
 - = 0 (censoring), if gallstones were not formed until last f/u

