14. CHANGE FROM PROTOCOL

Categor	Protocol	Statistical Analysis Plan	Reasons for
Determination of gallstones	The diagnosis of gallstone formation is based primarily on the results of abdominal ultrasound and is supplemented by abdominal CT scan results. If the results of the two tests differ, abdominal ultrasound result should be considered first for gallbladder gallstones, and both abdominal ultrasound and abdominal CT should be considered in the case of bile duct gallstones or intrahepatic bile duct gallstones.	The diagnosis of gallstone formation is based primarily on the results of abdominal ultrasound and is supplemented by abdominal CT scan results. If the results of the two tests differ,	Additional techniques for cases in which only abdominal CT scan results

Protocol No.: DW_UDCA005 English Translation Version

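### The SAP's primary endpoint mixes site and panel reads under an external-assessment label, and the protocol's own external endpoint is not reported at 12 months

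*Protocol*

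**What the plan says.** Protocol section 14.4.1 defines the primary endpoint as the percentage of patients with "gallstone formation within 12 months after gastrectomy according to the assessment by an external investigator". Section 11.2.8 says how three independent readers settle a case: "The assessment results on which at least two of the three external investigators agree on will be selected". Neither section lets the site's read replace the panel's.

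SAP section 6.1.1 repeats the external endpoint and the two-of-three rule, then attaches a footnote to the event definition. Subjects confirmed with gallstones by the institutional reviewer who "are terminated early from the clinical study, to be conservative, they are defined as subjects with gallstone formation regardless of the external" assessment. SAP section 8.4.1 and its table titles continue to describe the result as the external investigator's assessment.

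Three other provisions bear on this:

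- Protocol section 13.2: a gallstone confirmed by ultrasound during treatment ends participation at that point, and the subject counts as a completer.
- Protocol section 14.4.2 and SAP section 6.1.2, under time to gallstone formation: a stone found before 12 months leads to early termination, and a stone found at 12 months leads to completion.
- SAP section 6.1.2, secondary endpoint 2: "Percentage of subjects forming gallstone within 3, 6, and 9 months from gastrectomy as assessed by the external investigator". This stops at month 9.

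**The concern.** A reader of the results would take the primary table to be the two-of-three external read named in the protocol. For site-positive subjects who left before month 12 it is the site's read. At months 3, 6 and 9 the panel can add events but cannot remove one that the site has called. At month 12 it apparently can do both.

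The protocol's own endpoint is then not reported anywhere. Secondary endpoint 1 gives the site read to 12 months, and secondary endpoint 2 gives the external read only to 9 months. The sensitivity analyses in SAP sections 8.4 and 8.4.1 change the analysis set (PPS) or the treatment factor (three groups in one model), not the way an event is scored.

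At stake are what the trial can say about external confirmation of its primary result, the incidence estimates in every arm, and some power. Power matters because a failed 600 mg test also ends testing of 300 mg.

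**Working it through.** **1. Which rule applies at which visit, for a site-positive, panel-negative subject**

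| Scan | Status after the site read | Protocol 14.4.1 with 11.2.8 | SAP 6.1.1 |
|---|---|---|---|
| Months 3, 6, 9 | Early termination | Non-event | Event |
| Month 12 | Completion | Non-event | Non-event (inferred) |

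The last cell is an inference: the footnote's condition is early termination, and both documents class a stone found at month 12 as completion. No sentence expressly excludes month 12.

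**2. The plan's own sample size**

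Inputs from protocol section 8.3: two-sided 5% level, 80% power, 18% on placebo, 7% on study drug.

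n = (1.96 + 0.842)² × {0.07 × 0.93 + 0.18 × 0.82} / 0.11² = 138.01, stated as 138. With 20% dropout, 138 / 0.8 = 172.5, so 173 per group and 519 in total. The plan's figures reproduce.

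**3. Effect of the override on power**

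Let f be the share of panel-negative subjects whom the override turns into events, equal in all arms. The documents give no value for f, so it is an assumption shown over a range.

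- Observed rate: p* = p + (1 − p) × f
- Power: Φ( |p*C − p*T| / √[{p*C(1 − p*C) + p*T(1 − p*T)} / n] − 1.96 )

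For f = 3%, placebo is 0.18 + 0.82 × 0.03 = 0.2046 and active is 0.07 + 0.93 × 0.03 = 0.0979. The difference is 0.1067 and the variance sum is 0.1627 + 0.0883 = 0.2511. At n = 138 the standard error is 0.0427, so power is Φ(2.50 − 1.96) = 71%.

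| f (assumed) | Placebo | Active | Odds ratio | Power, n = 138 | Power, n = 173 |
|---|---|---|---|---|---|
| 0 | 18.0% | 7.0% | 0.34 | 80% | 88% |
| 1% | 18.8% | 7.9% | 0.37 | 77% | 85% |
| 2% | 19.6% | 8.9% | 0.40 | 74% | 83% |
| 3% | 20.5% | 9.8% | 0.42 | 71% | 80% |
| 5% | 22.1% | 11.7% | 0.47 | 65% | 75% |

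Both sample sizes matter. The FAS needs only one post-randomisation gallstone assessment, so the analysed number should lie between 138 and 173 per arm, apart from subjects whom the FAS rules exclude.

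**4. How disagreements would divide between the two rules**

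Assume a 1% chance of a site-positive, panel-negative read at each of the four scans. Months 3 to 9 give 1 − 0.99³ = 2.97%, scored as events. Month 12 gives 0.99³ × 0.01 = 0.97%, scored as non-events. About 75% of the disagreements (2.97 / 3.94) would be scored one way and 25% the other.

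**The case against.** The rule has a reason. A site-positive read ends follow-up, so if the panel disagrees there are no later images and 12-month status is unknown. At month 12 follow-up is complete and the panel can decide. This explains part of the difference between visits, but it does not make the result an external read or supply the missing pure-panel analysis.

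The rule is also written down in advance, reads are blinded, and equal disagreement across arms biases toward no effect. Calling it conservative is fair in that sense, and this is why the point is not graded higher.

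A reader might infer more than the documents support:

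- *That every conversion restores a site error.* A gallbladder stone requires movement of the echo with body position (protocol section 11.2.7), while the evidence a site must store is an ultrasound photograph (section 11.2.5). A panel working from stills might reject true stones, and the override would then correct panel misses.
- *That the power loss is established.* The disagreement rate is assumed, and the 18% and 7% come from published studies not described as centrally read, so they may already contain such error.
- *That a subject can be a non-event by 9 months and an event by 12 in the external endpoints.* SAP section 6.1.2 repeats the footnote, but its anchor is not visible in the text. It may belong to secondary endpoint 2, so the inconsistency is unproven.
- *That the SAP hides the change.* The legible part of SAP section 14 lists only the CT-only case ("Additional techniques for cases in which only abdominal CT scan results"), but the table is broken in the text and the omission cannot be proven.

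**Conclusion.** The point stands on the text. The protocol's primary endpoint is the two-of-three external read. The SAP analyses a hybrid of that read and the site's read, labels it external, and does not report the protocol's endpoint at 12 months. It is a hybrid, not a replacement: every subject who was not terminated early on a site-positive read is still scored by the panel.

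The different treatment of month 12 is a strong inference from the wording, not an explicit rule.

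The effect on power depends on the disagreement rate. Over an assumed 1% to 5% of panel-negative subjects converted, power falls from 80% to between 77% and 65% at 138 per arm, or from 88% to between 85% and 75% at 173. This rests on equal disagreement across arms and on the panel being right in each case. Under equal disagreement type I error is not inflated, so the text does not support calling the primary test invalid. Severity: should-fix.

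**What to change.** 1. Add a pre-specified FAS and PPS analysis of the pure two-of-three external read at 12 months, including the image that triggered termination. Score site-positive, panel-negative early terminators as non-events in one version and as missing in another. Both scorings are needed because a binary logistic model cannot treat a subject as followed only to a given scan.
2. State one rule for site-positive, panel-negative reads that applies at months 3, 6, 9 and 12, and state whether it covers secondary endpoint 2.
3. If the hybrid stays primary, relabel its tables as a combined site and panel endpoint, and record it in SAP section 14 as a change from the protocol before unblinding.

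Making the pure external read primary is possible but debatable, because the 12-month status of the discordant early terminators is unknown.

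The cost is SAP wording and a few extra tables. Follow-up of the discordant subjects stays truncated. Read beside the hybrid, the non-event and missing scorings show how far that can move each arm's proportion: hybrid highest, non-event lowest, missing in between.
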